6.4.4 Microbial DNA Sequencing

DNA will be prepared in the PennCHOP Microbiome Center. Samples will be sent to the center de-identified and coded with a study number. We will perform 16S rRNA and ITS gene sequencing to evaluate the bacterial and fungal microbiota, respectively, in rectal swab samples. Isolated DNA will be quantified using the Picogreen system and 50 ng of DNA will be amplified. Pyrosequencing will be carried out using barcoded primers as previously described⁴². For pyrosequencing of bacteria, primers annealing to the V1V2 region of the 16S bacterial gene will be used. The development of the ITS1 fungal primers is described in⁴². For pyrosequencing, we will

use the Roche/454 Genome Sequencer Junior. Sequence data will be processed using QIIME⁴³. If warranted by our preliminary data, we may analyze samples further using a metagenomic approach, in which DNA samples are nebulized, ligated to linkers, and subjected to pyrosequencing (IlluminaHiSeq). This allows enumeration of the types of genes present in a sample. To determine bacterial and fungal load, respectively, we will determine 16S and 18S gene copy number from the rectal swab samples. The qPCR methods including the details of the primers as well as PCR cycling conditions have been previously described⁴⁴.

6.4.5 Metabolic profiling based on plasma samples

Fasting glucose and oral glucose tolerance (on day 1 and 11), day 11 sera will be assayed for a standard comprehensive metabolic panel (includes albumin, urea, calcium, creatinine, glucose, and liver enzymes AST/ALT) performed at Penn's clinical lab. Additionally, sera will be assayed for a range of hormones and cytokines using a customized bead-based assay designed to include immune inflammatory and metabolic markers of obesity and type 2 diabetes (includes IL-8, IL-6, TNF α , lipocalin-2, MCP1, insulin, leptin, ghrelin, ESR, CRP) all of which are known to be elevated in metabolic syndrome (performed at GSU). Additionally, fecal samples will be assayed for lipocalin-2 by ELISA.

6.4.6 Long term sample storage and reuse of samples

All specimens remaining after the study is complete will be retained for possible future use unless specifically requested by the participant that the specimen be destroyed or it is deemed by the investigators that the specimens are no longer needed. Future studies, including genetic testing, may be conducted with residual samples.

7 Statistical Plan

7.1 Sample Size Determination

We will recruit the minimum number of subjects to provide adequate statistical power for the aims of the project. For aim 1, statistical power will depend on the prevalence of detectable CMC in the feces of participants at the end of follow-up. We anticipate that in the CMC treated group, the prevalence will be 100% and in the untreated group the prevalence will be 0%. However, with 8 subjects per group, we will have 89% power to detect a difference if the true prevalence of detectable CMC after 2 weeks of a high dose CMC and CMC free diet are 90% and 10%, respectively. For aim 2, power calculation were based on preliminary data in which the difference in mean distance of the nearest bacteria to the epithelium between patients with and without diabetes was 19.13 μ m. The within group standard deviation (SD) for patients without diabetes was 7.17. The within group SD for those with diabetes was even smaller. With a sample size of 8 subjects per group and assuming a within group SD of 7.17, we will have 90% and 80% power to detect a difference in the distance of the nearest bacteria to the epithelium between the treatment groups (CMC vs. no CMC) that is 35% and 44% smaller than the difference observed between patients with and without diabetes, respectively. In Aim 3, the study will have 80% power to detect a difference between

groups equal to 1.51 units of SD. For paired analyses within treatment groups, there will be 80% power to detect a difference of 1.15 units of SD.

7.2 Overview of Statistical Methods

Descriptive statistics (mean, SD, median, range, counts, and percentage) will be used to describe and compare (t-test or rank sum test for continuous variables and Fishers exact test for categorical variables) the baseline characteristics, usual diet, and immediate pre-enrollment diet between the treatment arms.

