4.4 Early Withdrawal of Participants

4.4.1 When and How to Withdraw Participants

Participants may be withdrawn from the study at any time if the investigator or the participant believes that the participant's safety will be jeopardized by continued participation, or if the participant does not follow study procedures. Likewise, participants will be withdrawn from the study if they withdraw consent.

5 Study Intervention

All foods will be prepared within the CHPS's metabolic kitchen without emulsifiers (unless specifically added). All participants will follow the same Western style diet (i.e. the only difference being portion size). The macronutrient percentages of calories for the study diet will be 55% carbohydrate, 30% fat, and 15% protein. The diet will be composed of two menus that will be consumed on alternating days. Water, coffee and tea will be provided as desired. Participants will have access to additional food outside of the meals provided, however, the entire serving of the previous meal must have been consumed. The additional food provided outside of the scheduled meals will consist of the food from the same Western style diet provided for each meal.

For the three days prior to admission, participants will be eating an emulsifier free diet at home. Food will be provided by the CHPS metabolic kitchen. After admission to CHPS, no emulsifiers will be consumed prior to dinner on Day 1. Thus, accounting for the 8 hours of nil per os status prior to admission, all participants will have approximately 80 hours of emulsifier free washout time prior to administration of the food containing CMC.

Participants will be randomly assigned to receive 0 or 15 gm per day of CMC (8 participants in each arm of the study). Beginning with the dinner meal on Day 1, all participants will consume one serving of brownie or sorbet (15 gm) per day that contain 0 or 2.5 gm CMC per serving. The brownie and sorbet servings will be provided at all three scheduled meals and scheduled snacks. Prior to eating any other food on the study menu, participants must consume the brownie and sorbet servings.

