6.2.2.2 Three Day Dietary Recall (Visit 1.1)

Data on recent dietary patterns will be collected for 7 days immediately prior to Visit 2. The participant will complete a diet diary during the week prior to Visit 2 that will be used to facilitate the dietary recall. Note that the last 24 hour recall for the day immediately prior to Visit 2 can be completed on the same day as Visit 2.

Three day dietary recalls will be performed by the CHPS bionutritionists. Dietary assessments are to be performed interactively using the Nutrition Data System program (University of Minnesota) that includes prompts for questions depending on the food item entered as part of the interview. Using this software, the diet information will be summarized according to the macronutrient composition (daily consumption of calories, protein, fat, carbohydrates and dietary fiber). Additionally, the data on fat and other macronutrients can be further subcategorized, such as according percent of calories from saturated, monounsaturated, and polyunsaturated fats.

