7.2.2 Comparison of metabolites between diets with and without CMC

The first analysis will compare the abundance of fecal and plasma metabolites between the two dietary groups. As assignment to the diet will be based on randomization, the primary analysis will be an unadjusted t-test to compare the concentration of the various metabolites measured in the plasma and feces. As there will be multiple comparisons, we will report both nominal (p values) and q values accounting for the multiple testing.

7.2.3 Effects of CMC consumption on a range of inflammatory and metabolic parameters that characterize metabolic syndrome

Weight change will be compared between the treatment groups from day 1 to day 11 using a t-test. If there is evidence of confounding despite randomization, additional analyses will use linear regression adjusted for change in weight from day 1 to day 11 and BMI at day 0.

We will also assess changes to each subject regarding satiety (from the questionnaire re food adequacy/sufficiency). These data are on visual analogue scale so will be compared using unpaired t-test for between group comparisons or paired t-tests for within group comparisons.

The area under the glucose and insulin concentration curves during the oral glucose tolerance test at day 1, day 11 and the change from day 1 to day 11 will be compared between groups using a t-test. The $\Delta I_{30}/\Delta G_{30}$ will be used as a measure of

beta cell function⁴⁵ while homeostasis model assessment of insulin resistance (HOMA-IR) will be used to estimate insulin resistance⁴⁶ and compared between the groups with a t-test at the same time points.

Sera will be assayed for a range of hormones and cytokines using a customized bead-based assay designed to include immune inflammatory and metabolic markers of obesity and type 2 diabetes (includes IL-8, IL-6, TNF α , lipocalin-2, MCP1, insulin, leptin, ghrelin, ESR, CRP) all of which are known to be elevated in metabolic syndrome (performed at GSU). Additionally, fecal samples will be assayed for lipocalin-2 by ELISA. These data will be compared using unpaired t-test for between group comparisons or paired t-tests for within group comparisons.

8 Safety and Adverse Events

Adverse Event

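### Baseline significance tests between randomised arms are uninformative, and the only adjusted analysis has an undefined trigger and a post-randomisation covariate

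*Combined protocol and SAP*

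**What the plan says.** Section 5 randomises participants to CMC or no CMC, with "8 participants in each arm of the study". Section 7.2 describes and also tests "the baseline characteristics, usual diet, and immediate pre-enrollment diet between the treatment arms". The tests are "t-test or rank sum test for continuous variables and Fishers exact test for categorical variables". Neither the number of variables nor the significance level is given. Section 6.2.2.2 shows that the dietary recalls alone supply "daily consumption of calories, protein, fat, carbohydrates and dietary fiber", and that fat and the other macronutrients can be subdivided further.

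Section 7.2.3 opens with a between-group t-test of weight change and continues: "If there is evidence of confounding despite randomization, additional analyses will use linear regression adjusted for change in weight from day 1 to day 11". The second covariate that it names is BMI, dated to a day 0. It does not say what counts as evidence of confounding, does not refer back to Section 7.2, and does not name the outcomes to be regressed. No other covariate set appears in the plan. Section 7.2.2 makes the primary metabolite comparison an unadjusted t-test.

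Section 6.2.2.3 says that food quantity will not be changed in response to weight gain or loss, because the emulsifier's effect on body weight is itself under study.

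**The concern.** There are three linked problems.

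- **The baseline tests answer a question that randomisation has already settled.** Any difference between the arms at baseline is chance. The p value does not say whether a gap matters for an outcome; that depends on how strongly the variable predicts the outcome. In a trial this small, sizeable gaps will also be non-significant and may be read as balance.
- **The adjusted analysis is optional on an unstated criterion.** Whether it exists will be decided after the data are seen, so an outcome may have one candidate result or two. The covariates do not depend on what was found: an imbalance in fibre, age or sex would lead to adjustment for BMI and weight change.
- **Weight change is not a baseline variable.** If CMC alters weight, adjusting for it can remove part of the effect being estimated.

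At stake are the power of the between-arm comparisons and the meaning of any adjusted estimate.

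**Working it through.** **Inputs.** 8 per arm (Sections 5 and 7.1); 80% power at 1.51 SD for Aim 3 (Section 7.1); tests from Section 7.2; covariates from Section 7.2.3. Two-sided alpha of 0.05 is assumed. Covariate-outcome correlations r of 0, 0.4 and 0.6 are assumed, because the documents give none.

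**1. The plan's own figure.** Two-sample t-test, df = 14, critical value 2.145, noncentrality 1.51 × √(8/2) = 3.02. Power is 80.2%, so the stated 80% reproduces.

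**2. Smallest gap that a baseline t-test can flag.** t(0.975, 14) × √(2/8) = 2.145 × 0.5 = 1.07 SD. This is an observed gap, in pooled SDs, for a continuous variable. The Study Summary lists 20 participants; with 10 per arm the figure would be 2.101 × √(2/10) = 0.94 SD. Fisher's exact test at 8 versus 8 needs a split such as 5 v 0, 6 v 1, 7 v 2 or 8 v 3. Its chance flag rate is 0.04% to 2.1% for prevalences of 10% to 50%.

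**3. Imbalance that passes.** The standard error of a chance gap is √(2/8) = 0.5 SD, so a gap above 0.5 SD occurs with probability 2 × (1 − Φ(1)) = 32%. By simulation, about 27% of trials have such a gap in a given covariate and a non-significant test.

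**4. Chance of at least one flag.** For k independent continuous tests this is 1 − 0.95^k: k = 10, 40%; k = 14, 51%; k = 20, 64%; k = 30, 79%. With k = 20 and pairwise correlation 0.3, 0.5 or 0.7, simulation gives 55%, 44% or 30%.

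**5. Power at 1.51 SD under three rules.** Simulation with 8 per arm and one baseline covariate. The middle column uses the regression result in 64% of trials (20 independent tests, any flag triggers) and the t-test otherwise.

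| r | Unadjusted | Regression in 64% of trials | Always adjusted |
|---|---|---|---|
| 0 | 80% | 78% | 76.5% |
| 0.4 | 80% | 82% | 83% |
| 0.6 | 80% | 87% | 92% |

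The middle column is close to a weighted mean: at r = 0.6, 0.64 × 91.6 + 0.36 × 80.2 = 87.5; at r = 0.4, 0.64 × 83.4 + 0.36 × 80.2 = 82.2. With no true effect, the rejection rate is about 5% under all three rules.

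**6. Timing of weight change.** Section 6.2.4.1 records Day 1 weight before the first meal. Section 5 starts CMC at dinner on Day 1. The change to day 11 therefore lies wholly after treatment begins, and Section 6.2.2.3 counts it among the effects to be evaluated. A variable that treatment may cause cannot confound a randomised comparison. If the regression were applied to weight change itself, the outcome would also be a covariate. The documents give no figures from which to size the resulting bias.

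**7. Timing of BMI.** The schedule in Section 6.2 passes from −1 to 1, so there is no day 0. BMI is documented at screening (Section 6.2.2.1), up to 60 days before admission. Weight is also measured at Visit 2 and on Day 1.

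**The case against.** Several stronger readings are tempting, and the defence is right to resist them.

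- **That the Section 7.2 tests are the trigger.** A reader might infer this, but the plan never says so. The t-test of weight change stands directly before the conditional sentence. Section 7.2.3 also compares day 1 glucose and insulin areas, the beta-cell index and HOMA-IR between arms, and Section 7.2 includes descriptive summaries. Any of these could be meant. This does not rescue the trigger: weight change cannot show confounding either, and under every reading the criterion is undefined and applied after the data are seen.
- **That some variable will be flagged by chance in most trials.** This needs at least 14 independent continuous tests, and more if they are correlated, as dietary variables are. The documents do not give the number.
- **That test-triggered adjustment costs about 11 points of power at r = 0.6 (81% against 92%).** That figure holds only if the flagged covariate is the one adjusted for, which happens in about 5% of trials. The plan's covariates are fixed. With a fixed covariate and a 64% trigger the gap is about 4 to 5 points at r = 0.6 and 1 point at r = 0.4.
- **That false positives are inflated.** Among trials with a non-significant gap above 0.5 SD and r = 0.6, the unadjusted test rejects a true null about 7% to 8% of the time. Over all randomisations it rejects 5%.

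The defence can add that the regressions are supplementary, so the unadjusted t-test is always reported; that Section 3.2 declares no pre-specified efficacy or safety endpoints and Aim 3 is exploratory; and that nothing in the documents shows BMI to be prognostic. All of this stands, and it limits the consequence. It does not supply a definition of the trigger or justify weight change as a covariate.

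**Conclusion.** The point holds as a minor defect of specification. Three parts rest on the text alone: baseline variables are significance-tested between randomised arms; the only adjusted analysis depends on an undefined criterion; and its fixed covariates include a post-randomisation variable that the protocol treats as a possible effect of the emulsifier.

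The 1.07 SD threshold is exact for a t-test at two-sided 0.05 with 8 per arm. The power gain depends on assumed correlations: 3 points at r = 0.4 and 12 at r = 0.6 compared with never adjusting, and 1 point and about 5 points compared with adjusting in 64% of trials. That gain comes from using a prognostic covariate, not from removing the baseline tests. The documents do not support a claim of inflated overall type I error, of a stated link between Section 7.2 and the trigger, or of a flag in most trials.

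**What to change.** - **Section 7.2:** report baseline characteristics and diet by arm with descriptive statistics only, and delete the tests and p values.
- **Section 7.2.3, trigger:** delete the condition about evidence of confounding. Keep the unadjusted t-tests. For each outcome in that section, add one between-arm linear regression, run whatever balance is observed.
- **Section 7.2.3, covariate:** fix in advance one pre-randomisation covariate that is already collected, for example baseline BMI. State the visit it comes from, since there is no day 0. Remove weight change from this model; it remains an outcome with its own comparison.

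This is a change of wording with no new data. Each regression spends one degree of freedom. If the covariate is unrelated to the outcome, power in the adjusted analysis falls by about 3.5 points (80% to 76.5% at 1.51 SD), while the unadjusted result is unaffected.

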7.2.1 Determining the effect of CMC on fecal and mucosal microbiome composition

We will first compare the bacteria taxa in each fecal stool communities sampled at baseline, after the 3 day emulsifier free period and during the intervention period (total of 96 stool samples and 16 biopsy samples per treatment arm – 8 participants on each diet) to determine within-diet and between-diet variation prior to the administration of antibiotics. The analyses will be conducted separately for microbiomes in fecal samples and also in colonic mucosa samples. We will employ both of our methods (PCoA and proportion of the community represented by different taxa) to summarize the data at each time point. Besides comparing the microbiome among the treatment groups at day 11, we will also perform repeated measurement analysis of variance (RM-ANOVA) to study the time effects on microbiome and potential time and diet interaction effects for our data on fecal samples. The outcomes of such RM-ANOVA are the significant principal components summarizing the bacterial taxa.

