6.1.4 Sigmoidoscopy to obtain mucosal biopsy samples

On days 1 and 11, each participant will undergo a sigmoidoscopy to obtain biopsies from the area of approximately 15 cm from the anal verge, which correlates with approximately the rectosigmoid junction. No bowel preparation will be utilized prior to the sigmoidoscopy since it is unknown what affect the bowel preparation may have on the fecal microbiome or the mucosally adherent microbiome. No sedation medications will be administered.

16 biopsies obtained from the distal 20 cm of the colon will be collected; 4 placed in Carnoy solution for non-denaturing confocal microscopy, 4 flash frozen in liquid

nitrogen, 4 placed in RNAlater, and 4 will be kept fresh for immediate cell isolation studies. Additional biopsies may be taken (up to a total of 20), to replace lost/dropped/unusable biopsies (i.e., if the biopsy is too small), for quality control and/or for methods testing.

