6.4.3 Microbiome characterization

Microbiota localization. For each subject, 4 distal biopsies, collected pre/post CMC and immediately preserved in Carnoy fixative, will be assayed by fluorescence microscopy to determine bacterial localization relative to the epithelium. Specifically, for each specimen, we will examine 5 high-powered fields, selected arbitrarily while blinded to the accompanying clinical data. We will use staining protocols developed by Gunnar Hansson and colleagues^{36, 37} that we have ourselves used extensively in our recent publications^{19, 38}. For each field, we will measure the distance of the 5 closest bacteria per field as illustrated in **Figure 2**. The 25 distances (5 per field x 5 fields) will then be averaged to produce the "average closest bacteria" and compared between groups as reported in our mouse-based studies^{19, 38}. **2) Microbiota composition.** Each fecal sample will be subjected to 16S, metagenomics, and meta-transcriptomic sequence-based analysis as previously described. Sequencing via the Illumina platform (Miseq for 16S, NextSeq500 for metagenomics/transcriptomic). Data will be processed and analyzed via the Qiime platform and R software, in a manner similar to our previous publications^{19, 38-40}. **3) Microbiota pro-inflammatory potential.** For each fecal sample collected, we will measure fecal levels of bioactive flagellin and LPS as reported in our previous publications^{19, 38, 40}. Briefly, for each sample, we will prepare a soluble surface extract to be generated by bead-beating followed by centrifugation. Such samples will be diluted and then applied to cells engineered to express receptors for TLRs 4 or 5 and produce peroxidase under the control of a NF- κ B responsive promoter - our initial publication using this technique describe an extensive set of control studies we have utilized to validate this approach⁴¹. These assays, standardized with E. coli flagellin and LPS will report the levels of bioactive LPS and flagellin, which we have shown are broadly reflective of a fecal specimens ability to drive pro-inflammatory gene expression upon injection into mice⁴¹. Comparison between groups will use t-test, repeated measures ANOVA or analogous non-parametric tests.

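### Section 7.2.1 plans a Day 11 mucosal composition comparison from 16 biopsies per arm, but section 6.4 assigns no composition assay to any biopsy and no stated between-arm test uses the Day 1 biopsies as baseline

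*Combined protocol and SAP*

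**What the plan says.** **Analysis side.** The Study Summary lists the effect of CMC on both fecal and mucosal microbiome composition. Section 7.2.1 takes this up: "The analyses will be conducted separately for microbiomes in fecal samples and also in colonic mucosa samples". It gives the material as a "total of 96 stool samples and 16 biopsy samples per treatment arm" and summarizes each time point by PCoA and by taxa proportions. The between-arm test is introduced with "Besides comparing the microbiome among the treatment groups at day 11". The same sentence adds repeated-measures ANOVA with time and time-by-diet effects, but only for the fecal data.

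**Laboratory side.** Section 6.4.3 states: "Each fecal sample will be subjected to 16S, metagenomics, and meta-transcriptomic sequence-based analysis as previously described". The only biopsies it assays are the Carnoy-fixed pieces, by fluorescence microscopy, for the distance of bacteria from the epithelium. Section 6.4.4 states: "We will perform 16S rRNA and ITS gene sequencing to evaluate the bacterial and fungal microbiota, respectively, in rectal swab samples". Sections 6.1.5 and 6.2 place the swabs on Day 1 only.

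**Collection side.** Section 6.1.4 states: "On days 1 and 11, each participant will undergo a sigmoidoscopy to obtain biopsies". Of the 16 pieces per visit, the allocation is "4 placed in Carnoy solution for non-denaturing confocal microscopy", four flash-frozen, four in RNAlater and four kept fresh for cell isolation. No section names an assay for the flash-frozen or RNAlater pieces.

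**The concern.** An analysis with a stated sample count, summary method and comparison day needs a measurement behind it. Here the statistical section counts biopsies as composition samples, while the laboratory section never turns a biopsy into taxa. The only mucosal samples with sequencing assigned are the swabs, and they precede the intervention, so they carry no information about CMC.

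There are two consequences. First, the tissue fraction, the handling of the four pieces per fraction, the sequencing method and the batch layout are all undecided. They could be settled after other results are known, in a 16-person trial that section 3.2 says has no pre-specified efficacy or safety endpoints. Second, even if the biopsies are sequenced, the only between-arm test stated for mucosa is a cross-sectional one at Day 11. Each participant's own Day 1 biopsy is collected and counted but left out of that test.

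Section 7.2.1 also still refers to a period before antibiotics, which this trial does not give. That suggests the section was not fully matched to this protocol.

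**Working it through.** **1. Reproduce the plan's counts.** Section 5 gives "8 participants in each arm of the study".
- Biopsies: 8 participants x 2 sigmoidoscopies = 16 per arm, which matches 7.2.1.
- Stools: Visit 2 plus Days 1 to 11 = 12 per participant; 8 x 12 = 96 per arm, which also matches.

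The 16 is therefore one biopsy sample per participant per visit, over both days.

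**2. Set each sample type against its assigned assay.**

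| Sample | Days | Assay assigned | Gives composition? |
|---|---|---|---|
| Stool | Visit 2, Days 1-11 | 16S, metagenomic, meta-transcriptomic (6.4.3) | Yes |
| Rectal swab | Day 1 | 16S, ITS, qPCR (6.4.4) | Yes, pre-intervention only |
| Biopsy, Carnoy | 1, 11 | Microscopy (6.4.3) | No, distance only |
| Biopsy, flash-frozen | 1, 11 | None named | Not specified |
| Biopsy, RNAlater | 1, 11 | None named | Not specified |
| Biopsy, fresh | 1, 11 | Cell isolation (6.1.4) | No |

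Sections 6.2.4.7, 6.2.4.8 and 6.2.4.10 give the Day 1 order: swab, then sigmoidoscopy, then the randomized diet at dinner.

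**3. Count the mucosal samples with sequencing assigned.**
- Day 1: swabs from 8 participants per arm.
- Day 11: 0.
- Biopsies: 0 of 16 per arm, so 0 of 16 x 2 = 32 in the trial.

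**4. Count the tissue with no stated use.** Each fraction has 8 x 2 x 4 = 64 pieces per arm. Flash-frozen plus RNAlater is 128 per arm, half of it from Day 11.

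**5. What the Day 1 biopsy could add.** Take one summary, such as a taxon's proportion, with variance s² at each visit and correlation r between visits. With n per arm, the variance of the between-arm difference is:
- Day 11 only: 2s²/n
- change from Day 1: 4s²(1 - r)/n
- adjusted for Day 1 (approximate): 2s²(1 - r²)/n

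Relative to Day 11 only, these are 1, 2(1 - r) and 1 - r². The documents give no r, so the values below are assumptions:

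| r (assumed) | Change | Adjusted |
|---|---|---|
| 0.3 | 1.40 | 0.91 |
| 0.5 | 1.00 | 0.75 |
| 0.7 | 0.60 | 0.51 |

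Change scores help only when r exceeds 0.5. Adjustment costs one error degree of freedom (14 to 13) and otherwise does not increase the variance.

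**6. Size of the repair.** One library per participant-visit is 16 x 2 = 32. Against 2 x 96 = 192 stool libraries, 32/192 = 16.7%. If the extra home stool before admission is also sequenced, the denominator is 16 x 13 = 208 and the share is 15.4%.

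**7. Power.** The Aim 2 calculation in 7.1 uses a difference of 19.13 µm and an SD of 7.17, both for bacterial distance by microscopy. Mucosal composition does not enter it.

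**The case against.** The best defence is that the intention is clear. Section 7.2.1 enters 16 biopsies per arm into a composition analysis, and 6.1.4 collects frozen and RNAlater tissue on both days. On that view only a laboratory sentence is missing. Much of this stands, and it rules out three stronger readings.

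- **A reader might infer that the comparison will have no data.** The documents do not show that. Suitable tissue is collected and counted. The figure of 0 of 32 counts explicit assay assignments and does not predict what will be sequenced.
- **A reader might infer that half of Aim 2 is lost.** Aim 2 in section 2 names gut microbiota composition, gene expression and/or localization, without naming mucosal composition. Section 3.1 speaks of stool composition and of localization. The mucosal comparison is a planned exploratory analysis.
- **A reader might infer that mucosa must share the stool platform and run.** Sections 6.4.3 and 6.4.4 do name different platforms (Illumina and Roche/454), but 7.2.1 analyses the two sample types separately, so comparability with stool is not required. The swabs fail because of their timing.

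It is also fair to say that 7.2.1 opens with a description of variation within and between diets, so the Day 1 biopsies are not wholly ignored. But no between-arm test stated for mucosa uses them. Intention also leaves fraction, method, pooling and batch undecided, and a missing assay sentence would not explain why repeated-measures analysis is confined to stool.

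**Conclusion.** The point holds as a conflict between sections 6.4 and 7.2.1, together with an inefficient comparison. As written, 0 of 32 biopsy participant-visits have a composition assay, the Day 11 mucosal comparison has no named data source, and the Day 1 biopsies do not serve as baseline. It should be corrected. It does not threaten the Aim 2 power statement or the stool analysis.

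This rests on three assumptions:
- There are 8 completers per arm. The Study Summary lists 20 participants; if all 20 were sampled twice, the count would be 40 participant-visits.
- The study outline figure, which is not shown in the available text, assigns no assay. Section 6.4 itself can be read from 6.4.1 to 6.4.6.
- The second biopsy is on Day 11, as 6.1.4 and 6.2.6.6 state. The schedule table, as extracted, seems to mark Day 10, which may be an extraction fault. The counts do not depend on it.

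The gain from using baseline depends on the between-visit correlation, which the documents do not give.

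**What to change.** 1. In 6.4.3 or 6.4.4, name the biopsy fraction to be sequenced (flash-frozen or RNAlater, whichever is not reserved for another use). Assign it to 16S sequencing for Day 1 and Day 11, and say how the four pieces per visit are handled. Process a participant's two visits in the same batch, so that batch differences do not enter the within-participant change. Include negative controls, as 6.1.5 already does for swabs with an air-exposed swab.
2. In 7.2.1, compare the arms on mucosal composition using the Day 1 value, by change from baseline or adjustment for it. Adjustment is the safer choice when the between-visit correlation is unknown. Remove the reference to antibiotics.
3. If the biopsies will not be sequenced, delete mucosal composition from the Study Summary and 7.2.1.

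Steps 1 and 2 cost about 32 extra 16S libraries (about 17% on top of the 192 stool samples in 7.2.1), plus tissue DNA extraction and negative controls, which that percentage leaves out. The tissue is already collected, so no extra procedure is needed and no power figure changes. Step 3 is a wording change at no cost.
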